Title

**The Effect of the Interaction of Glucagon and Insulin on Endogenous
Glucose Production in Humans**

Protocol Number: 20-001570

Principal Investigator: [name]

IND Sponsor: [name], # 116569 (Somatostatin)

Funded by: Intramural Funds

Version Number: 2

January 13, 2021

NCT: 04461015

Specific Aim: Determine the relative contribution of changes in insulin and glucagon concentration on endogenous glucose production in nondiabetic subjects.

1° Hypothesis: Hyperinsulinemia restrains the effect of rising glucagon concentrations on endogenous glucose production

2° Hypothesis: The % change in endogenous glucose production in response to rising glucagon concentrations is unchanged by hyperinsulinemia

Rationale: The experimental design we propose will enable the dissection of the relative contribution of insulin and glucagon concentrations to endogenous glucose production. Acquisition of this data will allow us to develop a model of insulin and glucagon contributions to postprandial glucose metabolism (1; 2).

A. Significance

Diabetes mellitus causes morbidity, mortality and costs in excess of ~\$170 billion/year(3). Therefore preventing diabetes is important. T2DM is characterized by defects in insulin secretion & action(4), and impaired postprandial suppression of glucagon(1; 2). Recently, we have shown that diabetes-associated variation in *TCF7L2* impairs postprandial suppression of glucagon secretion – an aspect of islet function that has been overlooked in prior genotype-phenotype correlation studies and in the pathogenesis of prediabetes(5). This indicates that the abnormal regulation of postprandial glucagon secretion and glucose tolerance in the TT subjects cannot be explained by alterations in β -cell function, in keeping with recent reports where glucagon secretion is independent of β -cell function(6). Taken together, these data imply that to accurately quantify the ability of the pancreas to lower glucose concentrations in the post-prandial period, we have to account for both β -cell and α -cell function. The oral minimal model uses knowledge of C-peptide kinetics to measure insulin secretion and quantify β -cell function. In a prior series of experiments (IRB # 17-006493), we quantified the contribution of glucagon suppression to endogenous glucose production in the setting of changing insulin concentrations. This experiment will provide information of how changing glucagon concentrations alter endogenous glucose production when insulin concentrations are constant.

B. Preliminary Data

[figure not shown]
[figure not shown]

Figure 1: Prior experiment with manipulation of insulin (0.6, 0.8 and 1.0 of an insulin profile) and glucagon

1. Glucagon alters postprandial glucose metabolism (2).
2. We have expertise in the design and conduct of clamp experiments (7; 8).
3. We have experience with the use of isotopes to measure glucose turnover (9).
4. Previously we utilized data from similar in vivo experiments to develop novel models of insulin secretion (10), hepatic insulin extraction (11) and the effect of Glucagon-Like Peptide-1 (GLP-1) on insulin secretion (12).
5. Data from IRB # 17-006493 demonstrate that with decreasing postprandial insulin concentrations, the effect of a lack of glucagon suppression on endogenous glucose production becomes more marked (**Fig.1,2**)

[figure not shown]
C. Research Design and Methods

Study Subjects: We will recruit 15 otherwise healthy subjects using intramural and local extramural advertising after approval from the Mayo Clinic Institutional Review Board. Individuals who express interest in participating will be invited for a screening visit. Individuals with a BMI < 19 or > 40 kg/m² will be excluded from the study to avoid potential confounding effects that may result from extreme leanness or from obesity. Subjects will have no known systemic illness, taking any medication that could affect glucose metabolism and no history of upper gastrointestinal surgery.

Exclusion Criteria: Subjects < 18 years of age or > 60 years of age will not be studied to minimize the potential confounding effects of age on glucagon and insulin action. The subjects will not be taking medications that affect glucose metabolism (to be determined by PI) and have no history of chronic illness or upper gastrointestinal surgery. We are seeking to recruit subjects who do not have diabetes (fasting glucose <100mg/dL).

Screening Visit: To ensure subjects are healthy, following written, informed consent, subjects will undergo a history and physical examination, vital signs, height, weight, blood collection (after an 8 hour fast) for complete blood count, creatinine, sodium, potassium, fasting glucose and urine collection for point of care pregnancy testing for females able to become pregnant. Subjects will be instructed to consume a weight maintenance diet (55% carbohydrate, 30% fat and 15% protein, caffeine free) for at least 3 days prior to each study visit. **Body Composition:** Body composition will be measured prior to participation using dual-energy X-ray absorptiometry (iDXA scanner; GE, Wauwatosa, WI).

Experimental Design: Volunteers will participate in a total of 2 protocols. The overnight studies will be performed at least a week apart in random order.

cannula will be inserted retrogradely into a vein of the contra-lateral dorsum of the hand. This will be placed in a heated Plexiglas box maintained at around 120°F to allow sampling of arterialized venous blood. At approximately 0600 (-180 min), a primed, (10 μ Ci prime, 0.1 μ Ci/min continuous) infusion containing trace amounts of glucose labeled with [3-³H] glucose will be started and continued till 0900 (0 min).

At 0900 (0 min), the infusion will be varied so as to mimic the anticipated pattern of fall of EGP. In addition, glucose also labeled with [3-³H] glucose will be infused so as to maintain glucose concentrations at ~ 95mg/dL. Peripheral venous glucose concentrations will be measured every 10 minutes to allow the infusion rate of glucose to be adjusted as necessary.

Simultaneously, an infusion of somatostatin (60ng/kg/min) will be started at time 0 to inhibit endogenous islet secretion and therefore ensure identical portal insulin concentrations on the two study days(8). Insulin will be infused at a constant rate known to produce ~ 50% suppression of EGP (0.4mU/Kg/min).

From 0900 (0 min) to 1030 (90 min) no glucagon will be infused. Subsequently, a glucagon infusion will commence (91 – 180 min) at 0.35 ng/Kg/min and then increase to 0.70 ng/Kg/min (181- 270 min), a rate which will be maintained till the end of the study (1330).

Study B (0.8mU/Kg/min): Approximately 1-2 weeks after the first study visit, subjects will be asked to return to the CRTU. This study visit will be similar to Study A. However, insulin will be infused at 0.8mU/Kg/min 0 to 270 minutes.

Analytical Techniques: All blood will be immediately placed on ice, centrifuged at 4°C, separated and stored at -80°C until assay. Glucose will be measured using a Yellow Springs glucose analyzer. Glucagon will be measured using an ELISA (Mercodia, Winston-Salem, NC). C-peptide will be measured using EMD Millipore (Billerica, MA) reagents. Insulin will be measured using a chemiluminescence assay with reagents obtained from Beckman (Access Assay, Beckman, Chaska, MN). [3-³H] glucose specific activity will be measured by liquid scintillation counting following deproteinization(14). Endogenous glucose production (EGP) and glucose disposal (Rd) will be measured as before(9; 15).

Study A (Insulin 0.4mU/Kg/min):

Subjects will be admitted to the CRTU at approximately 1700 on the day prior to study. They will then consume a standard 10kcal/kg meal (55% carbohydrate, 30% fat, 15% protein, caffeine free) and fast overnight. Blood will then be sampled for baseline enrichment and ²H₂O (1.67g/kg of body water) will be given in 3 divided doses at 2200, 2400 and 0200 (13). The following morning (approximately 0530), a forearm vein will be cannulated to allow infusions to be performed. In addition, a

Calculations: Glucose appearance and disappearance will be calculated using the steady-state equations of Steele et al., in which the actual tracer infusion rate for each interval is used in the calculation. The volume of distribution of glucose will be assumed to equal 200 ml/kg, and the pool correction factor assumed to be 0.65(16). Endogenous glucose production will be determined by subtracting the glucose infusion rate from the tracer-determined rate of glucose appearance(9). All rates of infusion and turnover will expressed per Kg/lean body mass.

Mean \pm SD	Detectable difference (0.4 vs. 0.8 insulin)	Detectable difference within each sub-group
Nadir EGP ($\mu\text{mol}/\text{kg}/\text{min}$)	3.9 ± 1.1	0.4 (10%)
AUC EGP ($\mu\text{mol}/\text{kg}$ per 5hr)	2816 ± 182	67 (2%)

Table 1: Pooled Means \pm SD used to estimate power. (Data from Ref. 1)

Statistical Analysis: A paired, two way student t-test (parametric) or a Wilcoxon matched-pairs

signed rank test (non-parametric) will be used to examine changes of EGP at the various time points of each study day. Differences between the 3 glucagon infusion rates will be assessed using a repeated-measures ANOVA which assumes the absence of a Gaussian distribution (Friedman test). Subsequently, in the presence of significant between group differences ($p < 0.05$), a *post-hoc* Student's t-test will used to examine differences between the 3 infusion rates of glucagon. If values are not normally distributed, a Dunn's test will be used instead.

Power calculation: Assuming similar variation to that previously observed(1), 60 subjects would provide approximately 80% power (at a 2-sided 0.05 α level), to detect small, biologically significant, differences in peak glucose, glucose area above basal and EGP in the presence and absence of glucagon suppression (Table 1, Col 3) as would 20 per subgroup (Table 1, Col 4).

D. Interpretation

We will accept our 1° hypothesis if endogenous glucose production (EGP) is higher during the 0.4 vs. the 0.8 study day. This would imply that despite rising glucagon concentrations higher insulin concentrations can still restrain EGP. It also will allow us to quantify the fold changes in EGP at low or high insulin concentrations.

To test our 2° hypothesis we will express EGP at 80, 180 and 270 minutes as a percentage of fasting EGP (0 min). The relative changes with increments in glucagon will demonstrate whether the relationship is linear or asymptotic. Comparison of the two study days will enable us to determine the effect of insulin on this relationship. We will accept our 2° hypothesis if % suppression at the 80, 180 and 270 minute time points does not differ between study days.

We will calculate changes in nadir and integrated rates of EGP, as previously described(17-20), to compare suppression between the two study days. We will also undertake exploratory analysis of the rates of glucose disappearance (Rd) to determine if differences in glucagon concentrations affect Rd as well as EGP.

Limitations / Precautions/ Additional or Alternative Analyses:

- Inhibition of glucagon secretion by somatostatin lowers portal concentrations. In the case of glucagon, an infusion that maintains peripheral concentrations of glucagon constant likely will result in a ~10% decrease in portal glucagon concentrations(21-23). However, in the current experimental design, the portal glucagon concentrations on the two study days will not differ.

E. Human Subjects

Detailed Description: Suitable volunteers will be asked to visit the CRTU on a total of 3 occasions, including screening. During the first or screening visit they will meet with a member of the study team and undergo a history and physical examination to ensure that they fulfill entry criteria. If eligible, they will be asked to undergo determination of body composition. After an overnight fast, a cannula will be placed to allow IV infusion. Infusions will be started on the study days. In addition a retrograde hand vein for blood draws will be placed. This hand will be placed in a Perspex hot-box heated to about 120 °F. Blood will be sampled several times (via the retrograde hand vein) to obtain arterialized venous samples.

Population: Subjects will be recruited using intramural and local extramural advertising after approval from the Mayo Clinic Institutional Review Board. The racial composition of the county is outlined in the table below (%) using data from the 2000 population census. No children or prisoners will be recruited.

	American Indian or Alaskan Native	Asian or Pacific Islander	Black, not of Hispanic Origin	Hispanic	White, not of Hispanic Origin	Other	Total
Female	0.15	2.8	1.8	1.5	43.8	0	51.5
Male	0.15	2.8	1.8	1.5	43.7	0	48.5
Total	0.3	5.6	3.6	3.0	87.5	0	100.0

Research Materials: We will be obtaining blood samples to measure hormone and glucose concentrations.

Recruitment of Subjects: Subjects will be recruited using IRB-approved advertising. Eligible subjects who express interest in participating in the study will be invited to the CRTU for a screening visit.

The following are exclusion criteria:

- Age <18 or >40
- BMI < 19 or > 28 kg/m²
- Medication that can affect glucose metabolism (determined by PI)
- Any chronic illness
- Upper GI surgery
- History of diabetes
- FBG >100 mg/dL
- For female subjects a positive pregnancy test

Potential Risks: Blood sampling. Blood samples are collected by venipuncture for this study. Bruising can occur with venipuncture, as can fainting, etc. Risk Monitoring / Risk Reduction: The samples are collected using aseptic technique in designated venipuncture areas of the CRTU where facilities are available should untoward reactions (fainting, etc.) occur. Given the aseptic nature of the sample collection and the small risk of bruising, the monitoring plan is focused on advising volunteers to call the investigators should they have unusual pain or discomfort from the venipuncture site. Blood drawn within a 12 week period will not exceed 550mL (one pint).

Vascular catheter placement. Catheter insertion, intravenous infusion and blood withdrawal are associated with a small risk of phlebitis. Risk Monitoring / Risk Reduction: This will be minimized by careful attention to sterile technique. If phlebitis occurs, it will be treated conservatively with heat and when appropriate, with antibiotics. The catheters will be cared for by experienced CRTU nurses in order to minimize the risk of these complications. In all protocols, “arterialized – venous” blood will be obtained by placing a hand in which a catheter has been inserted in a heated box during the study. The temperature inside the box is maintained at ~55°C. With prolonged exposure to continuous heat, there is a potential risk of local skin irritation or a minor burn. If this occurs, it will be treated appropriately. Catheter risks will be discussed with the volunteers prior to obtaining consent for the study.

Radiation. Subjects will be exposed to radiation in this study. Radioactive tracers will be used in the proposed studies. Lean body mass and percent body fat will be measured at the time of screening using DEXA (dual energy x-ray absorptiometry). Risk Monitoring / Risk Reduction: The lowest dose of radioactive tracers that can be reliably counted in plasma will be used. In all instances, the amount of radiation that a volunteer will receive will be well below levels that result in significant risk of harmful effects. Proposed radiation exposure will be reviewed by the Mayo Clinic Radiation Safety Board prior to initiation of any study. Women who could become pregnant will be required to have a negative pregnancy test prior to participation in each study utilizing radioactive tracers. The Mayo CRTU body composition core has a QDR4500 with fan scan technology which allows body composition to be performed in only a few minutes.

Deuterated Water. Deuterated water will be given in 3 divided doses at 2200, 2400 and 0200. Risk Monitoring / Risk Reduction: Deuterated water is sometimes associated with dizziness and vertigo which is reduced by giving the tracer in divided doses. The fact that it is given late at night while the patient is in bed will reduce the risk of falls. Prior experiments using deuterated water have suggested that the occurrence of this uncommon.

Infusion of Tracers, Hormones. All infusions carry a risk of allergic reactions, bruising, discomfort at the site of infusion, and infection. Risk Monitoring / Risk Reduction: All infusates are prepared by trained personnel (under the supervision of a research pharmacist) in a laminar flow cabinet using aseptic technique. Infusions take place on the CRTU where facilities are available should untoward reactions occur. Somatostatin infusion will be undertaken under the auspices of an IND obtained from the FDA. Somatostatin use can be associated with nausea and hypotension. In prior experience these effects are minor and disappear within minutes of cessation of somatostatin infusion. Insulin can lower the levels of glucose in the blood and cause symptoms of hypoglycemia. Plasma glucose will be monitored at regular intervals during study visits. Vital signs will be monitored hourly as per our standard practice during infusions in the CRTU.

Confidentiality. All studies expose participants to the psychosocial risks arising from any breach in confidentiality. The risks include anxiety, confusion, damage to family relationships or a compromised ability to obtain insurance or employment. These risks may not be confined to the individual but may extend to other family members. Risk Monitoring/Risk Reduction: The nature of the information obtained will be explained in detail to each participant. All information will be stored anonymously in the database and only the PI or one of his designates will have access to the data.

Data Safety and Monitoring Plan. The ultimate goal of this application is to further our understanding the role of different therapies in the management of diabetes. The DSMP utilized will adhere to the protocol approved by the Mayo Clinic IRB. We propose the following plan: -

Data quality and management: The principal investigator will review all data collection forms on an three-monthly basis for completeness and accuracy of the data as well as protocol compliance.

Adverse events grading: The common grading scale listed below will be used to grade AEs:

- 0 No adverse event or within normal limits or not clinical significant
- 1 Mild AE, did not require treatment
- 2 Moderate AE, resolved with treatment
- 3 Severe AE, resulted in inability to carry on normal activities and required professional medical attention
- 4 Life threatening or disabling AE
- 5 Fatal AE

Attribution scale: An adverse event includes both, an expected side effect that is of a serious nature, or an unexpected side effect/ event regardless of severity. All events will be graded as to their attribution (unrelated to protocol, or possibly, probably, or definitely related to protocol). Any event that is reported to either the principal investigator or his designated research associates by the subject or medical staff caring for the subject and which meets the criteria will be documented as such.

Data Monitoring. The majority of data generated from these protocols will be from analyses performed in our laboratory or the immunochemical core laboratory. Standard quality control procedures are in place for each assay. Genotyping results are examined for consistency between repeated genotypes of a given sample chosen at random. The frequency of data review for this study differs according to the type of data and can be summarized in the following table:

Data type	Frequency of review
Subject accrual (adherence to protocol regarding demographics, inclusion/exclusion)	Weekly
Adverse event/safety rates (injuries)	Weekly
Study data	Weekly
Annual report	Yearly for CRTU, IRB

Informed Consent. Written informed consent will be obtained from all individuals who participate in the study. The principal investigator or his co-investigators meet with each participant, review the consent form in detail and confirm the subjects understanding of the study. They answer all questions posed by the participants and when convinced that the subject verbally demonstrates understanding of the protocol obtains a signed consent. Only designated staff are authorized to obtain informed consent.

Benefits: This study exposes subjects to risks detailed above. However, as detailed it will advance our knowledge of how to treat diabetes and help make clinicians make rational therapeutic choices in the future.

F. Gender/Minority Mix

The majority of residents in Rochester, Minnesota and surrounding counties are White, recent population estimates from over the past decade have indicated that minorities make up a significantly larger segment of our communities. According to census area data such cultural groups as the Somalis, Hispanic/ Latinos, and South East Asians have increased the percentage of minorities living in Rochester and the surrounding counties from 3% in 1990 to nearly 10% in 2000. Despite the increases in the number of minorities within rural Rochester, Minnesota, it is likely that recruitment will fall short in the area of minority participation. However, we are actively working with the minority outreach specialist in the Center for Patient Oriented Research and Tribal Elders from the local minority populations, to develop complementary community-based strategies for recruitment of minorities at Mayo Clinic Rochester.

G. Bibliography

3. Albright AL, Gregg EW: Preventing type 2 diabetes in communities across the U.S.: the National Diabetes Prevention Program. *American journal of preventive medicine* 2013;44:S346-351

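### EGP is assigned to the steady-state Steele equations, but the constants given belong to the non-steady-state form, and the tracer plan covers only the fall in EGP

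*Combined protocol and SAP*

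**What the plan says.** Section C, Calculations, names the method: "Glucose appearance and disappearance will be calculated using the steady-state equations of Steele et al". It adds that each interval takes the tracer rate actually delivered. The next sentence supplies two constants: "The volume of distribution of glucose will be assumed to equal 200 ml/kg, and the pool correction factor assumed to be 0.65". EGP is then a difference: "Endogenous glucose production will be determined by subtracting the glucose infusion rate from the tracer-determined rate of glucose appearance".

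The Study A description in the same section sets the tracer plan from 0 min: "the infusion will be varied so as to mimic the anticipated pattern of fall of EGP". The clamp glucose carries the same tracer: "glucose also labeled with [3-³H] glucose will be infused so as to maintain glucose concentrations at ~ 95mg/dL". Insulin on that day is meant to halve EGP: "Insulin will be infused at a constant rate known to produce ~ 50% suppression of EGP (0.4mU/Kg/min". Glucagon is absent to 90 min, then runs at 0.35 ng/kg/min to 180 min and 0.70 ng/kg/min to 270 min. Study B is described as similar, with insulin at 0.8 mU/kg/min and no tracer pattern of its own.

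Under D. Interpretation, the primary hypothesis is accepted if EGP is higher on the 0.4 day. The secondary hypothesis compares EGP at 80, 180 and 270 min, as a percentage of the 0 min value, between days.

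**The concern.** The steady-state form is Ra = F/SA, where F is the tracer infusion rate and SA is plasma specific activity. It has no place for a volume or a pool fraction. Those enter only through the pVC × dSA/dt term of the non-steady-state form. Two analysts could follow the same paragraph and calculate EGP differently.

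The choice matters because the design moves EGP on purpose: down under insulin, then presumably up in two glucagon steps. If the tracer profile follows only the fall, unlabelled endogenous glucose dilutes SA during the rises, and F/SA reads too low. Using the actual tracer rate in each interval updates F but does not supply the missing dSA/dt term. Because EGP is Ra minus the glucose infusion rate, the whole absolute error in Ra passes into EGP. The result would be a blunted glucagon response, which bears on the fold changes, the AUC, the percentage-of-fasting comparison, and the plan's judgement of whether the glucagon response is linear or asymptotic.

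**Working it through.** **Yardsticks.** Table 1 gives nadir EGP 3.9, SD 1.1, detectable difference 0.4 µmol/kg/min; and AUC SD 182, detectable difference 67 µmol/kg. Taking each SD as that of a paired difference, n = [SD × (1.960 + 0.842)/δ]²:
- Nadir: (1.1 × 2.802/0.4)² = 59.4, so 60.
- AUC: (182 × 2.802/67)² = 57.9, so 58.

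This reproduces the plan's 60 subjects, so 0.4 and 67 can serve as the plan's own measure of a small difference.

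**Error of the steady-state form.**
- Steady state: Ra = F/SA.
- Non-steady state: Ra = [F − pVC × dSA/dt]/SA.
- Steady-state error = pVC × (dSA/dt)/SA.

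With the plan's constants, V = 200 ml/kg = 2 dL/kg, so pVC = 0.65 × 2 dL/kg × 95 mg/dL = 123.5 mg/kg = 685.5 µmol/kg.

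| SA drift (assumed) | Error, µmol/kg/min |
|---|---|
| none | 0 |
| 3.5% per 60 min | 685.5 × 0.035/60 = 0.40 |
| 10% per 90 min | 685.5 × 0.10/90 = 0.76 |
| 5% per 30 min | 685.5 × 0.05/30 = 1.14 |

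The error has the sign of the drift: falling SA understates EGP.

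**Simulation.** One glucose pool, both days. These inputs are assumptions and are not in the documents:
- basal EGP 10–14 µmol/kg/min;
- EGP falling to 50% of basal (0.4 day) or 25% (0.8 day), then rising to 65% and 85%, or 35% and 50%, after the two glucagon steps;
- a 20-minute time constant for each shift in EGP;
- Rd plateau 20 or 35 µmol/kg/min;
- true p 0.5–0.8;
- infused glucose labelled at basal SA;
- SA sampled every 10 min.

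Results for pure F/SA:
- Tracer tracks EGP throughout: error 0 on both days.
- Tracer follows only the fall, with a day-specific fall:

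| | 0.4 day | 0.8 day |
|---|---|---|
| 180 min | −0.14 to −0.47 | −0.02 to −0.12 |
| 270 min | −0.22 to −0.79 | −0.04 to −0.18 |

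- The largest transient error was 0.5 to 1.9. The AUC difference between days shrank by about 55–116 µmol/kg, or 92–199 if one 50% fall pattern served both days. With that shared pattern the 0.8 day was also overstated at 80 min, by up to 0.26.

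One case in full (basal 14, p = 0.65, day-specific fall):
- At 270 min, true EGP is 11.87 and 6.98, a difference of 4.89. F/SA gives 11.87 − 0.56 = 11.31 and 6.98 − 0.11 = 6.87, a difference of 4.44.
- As a percentage of fasting, 85 and 50 become 81 and 49, so the gap falls from 35 to 32 points.
- On the 0.4 day the 80-to-270 min fold rise drops from 11.87/7.13 = 1.66 to 11.31/7.13 = 1.59.

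**With the pV term at p = 0.65.** Under the same drift, the largest error is about 0.13–0.44, part of it from 10-minute differencing across a glucagon step, and the AUC error is at most about 43 µmol/kg per day. What remains depends on p: if true p is 0.5–0.8, a 5% drift over 30 min leaves ±0.15 × 200 ml/kg × 5.27 µmol/ml × 0.05/30 = ±0.26.

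**The case against.** The best defence is that the label is a slip. V and p serve no purpose unless the dSA/dt term is applied, so the correction may well be intended. The design also works against drift: the tracer is varied from 0 min, the clamp glucose is labelled, and the methods paper cited for EGP (reference 9) names constant specific activity in its title. If SA is held constant, the equation makes no difference. All of this stands. A reader might infer that EGP will certainly be calculated without correction, or that it is certainly biased by different amounts on the two days. The documents support neither: the first is one of two readings, and the second depends on a drift they do not quantify.

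Larger errors are easy to produce. An assumed 30% drift over 90 min gives 685.5 × 0.30/90 = 2.3 µmol/kg/min, or 59% of the planning nadir. Nothing in the documents supports that drift. The figure exceeds every simulated error, and the nadir is the wrong denominator for an error that arises while glucagon is raising EGP. The 80, 180 and 270 min readings also fall late in each step, when transients have partly settled. Finally, 0.4 is the detectable difference for 60 subjects, whereas the plan recruits 15. On the same SD, 15 subjects would detect about 0.86, so an error of 0.4 is less prominent against what the study can resolve.

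The defence does not remove the contradiction. It also leaves the glucagon steps and the 0.8 day without a described tracer pattern, and the plan states no tolerance or check for SA drift.

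**Conclusion.** Wrong as written; moderate severity. The named equation and the stated constants cannot both describe the calculation. Read literally, the steady-state rule misstates EGP whenever SA drifts. The error is zero with no drift and reaches the plan's own 0.4 µmol/kg/min at 3.5% per hour. If the tracer follows only the fall, the assumed kinetics give errors at 180 and 270 min of about −0.14 to −0.79 on the 0.4 day and −0.02 to −0.18 on the 0.8 day.

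A reader might conclude that the primary finding could be overturned. That is not supported: in no simulated scenario did the 0.4 versus 0.8 difference change sign, and in the fall-only scenarios it shrank. What is exposed is size: the AUC, the fold change, the shape of the glucagon response, and the percentage-of-fasting comparison. For that comparison, a narrowed gap leans towards accepting a hypothesis of no difference. These sizes rest on assumed EGP and Rd courses; the arithmetic for pVC uses only the plan's constants and clamp target.

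**What to change.** 1. In Calculations, replace the steady-state label with the non-steady-state Steele equation, using the stated V and p and the actual tracer rate in each interval. It equals the steady-state form when drift is zero, so nothing is lost. This is a wording change that uses the same samples and constants, and it should be made before EGP is calculated.
2. Report SA by glucagon step and study day, so that readers can see how much the correction matters.
3. Add a sensitivity analysis over p, for example 0.5 to 0.8. This costs a rerun of the calculation.
4. Reconcile the tracer-profile sentence with the two glucagon steps and with each insulin day. This sentence governs study conduct, so it is more than an analysis edit. If visits have already taken place, record the profile actually used on each day.

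### The 0.4 versus 0.8 mU/kg/min day comparison has no period term and no stated method of allocating visit order; under random order this costs precision, not validity

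*Combined protocol and SAP*

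**What the plan says.** All of the following is in the combined protocol and SAP.

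- **Order of visits.** Section C, Experimental Design: "The overnight studies will be performed at least a week apart in random order". No ratio, blocking or method of allocation is given. The number recruited is 15 ("We will recruit 15 otherwise healthy subjects", Study Subjects).
- **Study B (0.8 mU/kg/min).** "Approximately 1-2 weeks after the first study visit, subjects will be asked to return to the CRTU". The visit is then described as a variation on Study A.
- **Tests.** Section C, Statistical Analysis: "A paired, two way student t-test (parametric) or a Wilcoxon matched-pairs" signed-rank test "will be used to examine changes of EGP at the various time points of each study day". The glucagon steps within a day have their own method: "Differences between the 3 glucagon infusion rates will be assessed using a repeated-measures ANOVA", in Friedman form with post-hoc tests. Period, visit, sequence and carry-over are not mentioned.
- **Decision rules.** Section D rests both hypotheses on the contrast between days. Primary: "We will accept our 1° hypothesis if endogenous glucose production (EGP) is higher during the 0.4 vs. the 0.8 study day". Secondary: "We will accept our 2° hypothesis if % suppression at the 80, 180 and 270 minute time points does not differ between study days".

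**The concern.** When each subject is studied twice in random order, a systematic difference between first and second visits enters the within-subject insulin difference with a plus sign in one sequence and a minus sign in the other. A plain paired test cannot separate this from noise. Two things follow. The spread of the paired differences grows, so power falls. And if the two sequences differ in size, part of the visit effect stays in the estimate for that particular trial.

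The secondary hypothesis adds to the concern. It is accepted when no difference between days is found, so added noise makes acceptance easier.

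Separately, Study B is written as the visit to which subjects return. Site staff could take that to mean that the 0.4 day always comes first, which is not what Experimental Design says.

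**Working it through.** **1. Which test serves the day contrast.** The sentence describing the paired test does not name the 0.4 versus 0.8 comparison. The Friedman test covers the three glucagon rates, so the paired test is the only stated method left for the comparison that section D needs. This is an inference.

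**2. The plan's own figure.** Table 1 gives nadir EGP 3.9 ± 1.1 µmol/kg/min and a detectable difference of 0.4; the power statement gives 60 subjects, 80% power and two-sided 0.05. The paired formula n = (SD × (1.96 + 0.84) / difference)² gives (1.1 × 2.80 / 0.4)² ≈ 59.4, so 60. The stated figure is reproduced as a plain paired calculation, with 1.1 acting as the SD of the difference and no period term. The gap between 60 and the 15 recruited is a separate matter. Here n = 15 is used, at which the difference detectable with 80% power by the paired t-test is 0.86.

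**3. Assumptions.** The SD of the paired difference is 1.1 (Table 1 says only that its SDs are pooled). The true insulin difference is 0.86. The visit effect π (second minus first visit) is not given anywhere, so it runs from 0 to 1.0 µmol/kg/min, up to 1.0/3.9 = 26% of mean nadir EGP.

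**4. Chance bias in a given trial.** Bias = π × (n1 − n2)/15, that is 1/15 of π at 8/7, 5/15 at 10/5 and 7/15 at 11/4. With unblocked randomisation (binomial, 15 subjects, probability one half), a split of 10/5 or worse has probability 30%, and 11/4 or worse 12%. The bias averages zero over the randomisation.

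**5. Precision.** The visit effect inflates the SD of the difference by about √(1 + π²/1.1²). Simulated results at an 8/7 split follow. The power range reflects whether the residual π/15 works against or with the insulin effect.

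| π | SD factor | Paired-t power | Paired-t type I error | Power with period term |
|---|---|---|---|---|
| 0 | 1.00 | 80% | 5.0% | 80% |
| 0.2 | 1.02 | 78–81% | 4.7% | 80% |
| 0.4 | 1.06 | 74–79% | 3.9% | 80% |
| 0.8 | 1.24 | 57–70% | 1.9% | 80% |
| 1.0 | 1.35 | 46–63% | 1.1% | 80% |

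Under simple, unblocked random order, type I error of the paired t-test stays at about 5% for every π. Its power is 79%, 75%, 62% and 54% at π = 0.2, 0.4, 0.8 and 1.0.

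**6. Price of the period term when there is no visit effect.** The standard error changes from 1.1/√15 = 0.284 to 1.1 × √((1/n1 + 1/n2)/4), and the degrees of freedom from 14 to 13.

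| Split | Standard error | Power |
|---|---|---|
| Paired t, any split | 0.284 | 80.4% |
| Period term, 8/7 | 0.285 | 79.8% |
| Period term, 10/5 | 0.301 | 75% |
| Period term, 11/4 | 0.321 | 70% |

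**The case against.** The strongest reply is that a plain paired analysis of a small crossover in random order is valid, and that a period term only refines it. That stands. A reader might infer that the planned test is biased or has inflated type I error. Over the randomisation it is neither. An error rate of 16% can be produced, but only by fixing the split at 11/4 and assuming a visit effect of 1.0; at 8/7 with the same effect the test is conservative, at about 1%.

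A reader might also infer that the order is in fact fixed, so that visit and insulin rate are fully confounded. The documents do not support this. Experimental Design states random order outright. The Study B text speaks of the first study visit, not of Study A, and its comparison with Study A concerns procedures. What remains is a wording conflict to be reconciled.

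The size of any visit effect is unknown and may be small. Diet is standardised before each visit, and the evening meal, overnight fast, somatostatin and glucose target are the same on both days. The secondary analysis divides by fasting EGP, apparently from the same day, which would remove a visit effect that acts proportionally. These points also stand: at 0.4 or below and an 8/7 split, the loss is modest. They do not show that the effect is nil, and they do not supply the missing allocation method.

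**Conclusion.** The point holds as one of precision and clarity. With order truly random, the planned test gives a valid comparison of the insulin days, but it leaves any visit effect in the error term and, with no stated balancing, leaves the trial open to chance bias of up to about half the visit effect at an 11/4 split (7/15). At 8/7 the power loss ranges from negligible at a visit effect of 0.2 to between 17 and 34 percentage points at 1.0. For the secondary hypothesis the direction is clear, since noise favours acceptance, but the figures above are for nadir EGP and do not carry over directly to percentage suppression.

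The sizes rest on an assumed visit effect, on reading Table 1's 1.1 as the SD of the paired difference, on a true difference of 0.86, and on the inference that the paired test is meant for the day contrast. The missing allocation method and the ambiguous Study B wording rest on no assumption. This should be corrected, but it does not undermine the design.

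**What to change.** 1. State that the two sequences are allocated in balanced blocks, giving 8/7 among 15 subjects.
2. Name the test for the 0.4 versus 0.8 contrast and include a period term. A simple form takes each subject's first-minus-second-visit difference and compares the two sequence groups; half the difference between the group means is the insulin effect. Equivalently, average the mean 0.4-minus-0.8 difference of the two sequences with equal weight. (Testing the 0.4-minus-0.8 differences of one sequence against those of the other would test the visit effect instead.) A rank-sum version of the first form can replace the signed-rank test.
3. Reconcile the Study B text with Experimental Design, for example by calling it the other study visit.

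The cost is wording and one degree of freedom: about 79.8% against 80.4% power at 8/7 if there is no visit effect. Steps 1 and 2 belong together, because without blocking the period term can itself cost power (75% at 10/5, 70% at 11/4). Dropouts that unbalance the sequences would have the same effect.
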